5.4.2 Discontinuation of Entire Study

AbbVie may terminate this study prematurely, either in its entirety or at any study site, for reasonable cause provided that written notice is submitted in advance of the intended termination. The Study Investigator may also terminate the study at his/her study site for reasonable cause, after providing written notice to AbbVie in advance of the intended termination. Advance notice is not required by either party if the study is stopped due to safety concerns. If AbbVie terminates the study for safety reasons, AbbVie will immediately notify the Study Investigator by telephone and subsequently provide written instructions for study termination.

AbbVie reserves the right to discontinue the study at any time and to remove all study materials from the study site. Possible reasons for termination of the study include, but are not limited to:

- Safety concerns based on reported data
- Unsatisfactory enrollment with respect to quantity or quality
- Inaccurate or incomplete data collection
- Falsification of records
- Failure to adhere to the protocol

5.5 Treatments

5.5.1 Treatments Administered

All treatments administered will be assigned via Interactive Response Technology (IRT) in order to maintain blinding. During Period A (Week 0 through Week 12), all subjects will receive 4 injections initially at Day 1 (or alternatively, given as two 0.8 mL injections per day on 2 consecutive days), 2 injections at Day 15 (Week 2), and one injection weekly

from Week 4 through Week 12. During Period B, all subjects will receive one injection weekly from Week 13 through Week 14. During Period C, all subjects will receive one injection weekly from Week 15 through Week 23. No study drug will be administered at the Week 24 or Premature Discontinuation Visit.

Study drug will be provided as a sterile, preservative-free solution for subcutaneous (SC) administration in 1 mL pre-filled syringes containing adalimumab 40 mg/0.8 mL or placebo (0.8 mL). The subject should be instructed to store the pre-filled syringe in the outer carton (in order to protect from light) in the refrigerator at 2° to 8°C/36° to 46°F, and that syringes should not be stored in a freezer.

Study drug will be administered SC using sterile technique by the subject or designee (e.g., family member, friend, health care professional) at the study site, or at home via self-injection following proper training ([Appendix P](#)) or by a qualified designee. At each Study visit qualified research personnel will observe the subject or designee during the injection to ensure proper technique. The subject should place the used syringe in the sharps disposal container, which will be provided to the subject at each study visit (unless prohibited by local regulations) or less frequently depending upon the size of the container.

Period A

Subjects randomised to Arm 1 will receive:

- 160 mg/3.2 mL adalimumab at the Baseline Study visit (Day 1) administered as four 40 mg injections SC (or two 0.8 mL injections on two consecutive days, i.e., Day 1 and Day 2)
- 80 mg/1.6 mL adalimumab at the Week 2 (Day 15) Study visit administered as two 40 mg injections SC
- 40 mg/0.8 mL adalimumab every week (ew) from Week 4 (Day 29) through Week 12 administered (either at the Study visit or at home as appropriate) as one 40 mg injection SC

Subjects randomised to Arm 2 will receive:

- 3.2 mL placebo at the Baseline Study visit (Day 1) administered as four 40 mg injections SC (or two 0.8 mL injections on two consecutive days, i.e., Day 1 and Day 2)
- 1.6 mL placebo at the Week 2 (Day 15) Study visit administered as two 0.8 mL injections SC
- 0.8 mL placebo every week (ew) from Week 4 (Day 29) through Week 12 administered (either at the Study visit or at home as appropriate) as one 0.8 mL injection SC

Period B

Subjects randomised to Arm 1 will receive:

- 40 mg/0.8 mL adalimumab every week (ew) from Week 13 through Week 14 administered (either at the Study visit in clinic, in hospital, or at home as appropriate) as one 40 mg injection SC

Subjects randomised to Arm 2 will receive:

- 0.8 mL placebo every week (ew) from Week 13 through Week 14 administered (either at the Study visit in clinic, in hospital, or at home as appropriate) as one 0.8 mL injection SC

Period C

Subjects randomised to Arm 1 will receive:

- 40 mg/0.8 mL adalimumab every week (ew) from Week 15 through Week 23 administered (either at the Study visit or at home as appropriate) as one 40 mg injection SC

Subjects randomised to Arm 2 will receive:

- 0.8 mL placebo every week (ew) from Week 15 through Week 23 administered (either at the Study visit or at home as appropriate) as one 0.8 mL injection SC

5.5.2 Identity of Study Drug

The individual study drug information is presented in [Table 2](#).

Table 2. Identity of Study Drug

Study Drug	Formulation	Manufacturer
Adalimumab	40 mg/0.8 mL pre-filled syringes Adalimumab/Mannitol, Citric acid monohydrate, Sodium citrate, Disodium phosphate dehydrate, Sodium dihydrogen phosphate dehydrate, Sodium chloride, Polysorbate 80, Water for injection, Sodium hydroxide added as necessary to adjust pH	AbbVie
Placebo	0.8 mL pre-filled syringes Mannitol, Citric acid monohydrate, Sodium citrate, Disodium phosphate dehydrate, Sodium dihydrogen phosphate dehydrate, Sodium chloride, Polysorbate 80, Water for injection, Sodium hydroxide added as necessary to adjust pH	AbbVie

Each study site will be responsible for tracking the lot numbers and expiration dates for all non-investigational medicinal products (e.g., generic name and generic name) that are dispensed.

5.5.2.1 Packaging and Labeling

Adalimumab and placebo will be provided in a 1 mL pre-filled syringe containing adalimumab 40 mg/0.8 mL or matching placebo injection solution and will be packaged in two pre-filled syringes per carton. Each adalimumab/placebo kit carton and syringe will be labeled and have a unique kit ID. The labels for the adalimumab/placebo syringe kit carton will minimally contain the required country information.

Each label must remain affixed to the dosing unit.

5.5.2.2 Storage and Disposition of Study Drugs

Adalimumab/placebo pre-filled syringes are to be stored protected from light at 2° to 8°C/36° to 46°F. Study drug ***must not be frozen*** at any time. A storage temperature log is to be maintained to document proper storage conditions. The refrigerator temperature must be recorded on a temperature log to record proper function. Malfunctions or any temperature excursions must be reported to the Sponsor immediately upon identification. Study medications should be quarantined and not dispensed until AbbVie GPRD or Abbott Temperature Excursion Management System (ATEMS) deems the medications as acceptable.

All clinical supplies must be stored and locked in a secure place until they are dispensed for subject use or are returned to AbbVie.

Study drugs, syringes, and associated products are for investigational use only and are to be used only within the context of this study.

5.5.3 Method of Assigning Subjects to Treatment Groups

The randomisation schedules will be generated at AbbVie before the start of the study and will be provided to the IRT vendor. Before the study site is initiated, the instructions for use of the IRT will be provided to the site. All subjects will be assigned a unique identification number by IRT as they are screened for the study. The subjects will be randomised centrally and stratified by Hurley Stage (II versus III) and anatomical location of the HS surgical site (i.e., axilla versus inguinal region) in a 1:1 ratio to either adalimumab or placebo at Day 1. The number of subjects in Hurley Stage III is not to exceed 50% of the total planned number of subjects (100 subjects). In addition the number of subjects with an AN count of 3 or 4 is not to exceed 40 (20% of the total planned number of subjects).

5.5.4 Selection and Timing of Dose for Each Subject

Subjects should take study medication as outline in Section 5.5.1.

At the Baseline visit, after all assessments have been completed, subjects in Arm 1 will receive four injections of active study drug (40 mg/0.8 mL each) and subjects in Arm 2 will receive four placebo injections (0.8 mL each) as detailed in Section 5.5.1.

Appropriate study site personnel will train and then supervise the subject or designee administering at least one injection of the study drug to ensure proper understanding of injection technique (Appendix P). The subject or designee will subsequently dose and be witnessed by study site personnel during their study visits to ensure continued proper technique. When study drug is administered at the Day 1 (Week 0) and Week 2 study visits (see Appendix C), the subject should remain at the study site for approximately 15 to 30 minutes after injection for observation.

For home administration of injection, subjects or qualified designee will be instructed to inject study medication on the same day of the week as their Baseline visit day as detailed in Section 5.5.1. Every kit contains 2 syringes each.

If a subject should forget to administer the injection of study medication on their regularly scheduled dosing date, the subject should take the forgotten injection as soon as she/he remembers the dose was missed up to the day before the next scheduled dose. The subject should not administer two doses on the same day.

Doses not administered (e.g., not taken before the next dose is scheduled), should be recorded as not taken in the source. The extra dose should be returned in its entirety to the study site at the subject's next study visit. Meanwhile, the subject should resume their regular dosing schedule based on the first dosing date at Baseline (Day 1).

In the event the incorrect dose is taken, the entire volume of study drug is not injected, or a dose is missed, the subject should be instructed to contact the study site to determine how to proceed with dosing. The subject must record all dosing information on the Subject-Dosing Diary Sheet.

5.5.5 Blinding

5.5.5.1 Blinding of Study Drug

All AbbVie personnel with direct oversight of the conduct and management of the trial (with the exception of AbbVie's Global Drug Supply Management Team); the Study Investigator, the designated surgeon, and study site personnel; and the subject will remain blinded to each subject's treatment throughout the study. The IRT will provide access to blinded subject treatment information in the case of medical emergency. The procedure for breaking the blind is referenced in the IRT Training Slides provided to each study site.

AbbVie must be notified before the blind is broken unless identification of the study drug is required for medical emergency, i.e., situation in which the knowledge of the specific blinded treatment will affect the immediate management of the subject/patient's conditions (e.g., antidote is available). AbbVie must then be notified within 24 hours of the blind being broken. See Section 7.0 for contact information, including 24/7 physician coverage.

The date and reason that the blind was broken must be conveyed to AbbVie and recorded in the source documentation and on the appropriate eCRF.

5.5.6 Treatment Compliance

The Study Investigator or his/her designated and qualified representatives will administer/dispense study drug only to subjects enrolled in the study in accordance with the protocol. The study drug must not be used for reasons other than that described in the protocol.

The subject or his/her qualified designee will administer all doses of study drug after being appropriately trained (see Section 5.5.4). Appropriate study site personnel will supervise the subject's administration of the study drug at required study visits (see [Appendix C](#)) to ensure proper injection technique. In order to document compliance with the treatment regimen, the subject will be given a dosing sheet ([Appendix Q](#)) to record all injection dates and times. Compliance information will be document on the appropriate

eCRF. The subject will be counseled on missed doses of study drug. If the subject does not return the dosing sheet, study drug boxes, and/or sharps containers (when applicable), study site personnel should question the subject and obtain as much information as possible as to the dosing of the study drug.

The information should be documented on the source documents as per "best recollection" and when possible, re-verified when the dosing sheet is returned before completing the applicable eCRF page.

If a subject is consistently not returning the dosing sheet, not providing accurate dosing information, or consistently missing doses and/or is deemed non-compliant with no explanation, the situation will be discussed with the AbbVie Study Designated Physician and the subject may be discontinued from the study.

5.5.7 Drug Accountability

The Study Investigator or designee will verify that study drug supplies are received intact, at the appropriate temperature, and in the correct amounts. This will be accomplished by documenting the condition of the shipment, verifying kit numbers in the package against the Proof of Receipt (POR) or similar document included with each drug shipment, and documenting this verification by signing and dating the POR or similar document. The original POR or similar document will be kept in the study site files as a record of what was received.

In addition, an accurate running inventory of study drug will be kept by the study site using the online clinical drug accountability (CDA) system provided by the IRT system. The CDA system will track the following: date received, the lot number, the kit number(s), date dispensed, subject number, and the identification with date of the person dispensing the drug.

All empty study drug boxes and used pre-filled syringes will be inventoried by the study site personnel. Each subject will be given his/her own sharps disposal container to store used pre-filled syringes. Empty study drug boxes and sharps disposal containers should

be returned by the subject at each study visit for accountability and compliance purposes, and new containers will be issued as necessary. Empty study drug boxes and returned sharps disposal containers will be retained (unless prohibited by local regulations) until the AbbVie Medical Monitor is at the study site to confirm the returned study drug. The AbbVie CRA and study site personnel will complete study drug accountability using study drug logs, source documents, and subject dosing sheets plus visual inspection of empty study drug boxes and the syringes in the returned sharps disposal containers. The returned sharps disposal containers should never be opened. Once the AbbVie CRA has verified drug accountability, the study site personnel and AbbVie CRA will document that the used syringes have been destroyed, using appropriate biohazard precautions, when appropriate. A copy of the destruction methodology should be maintained at the study site's facility. Unused study drug will be returned by the AbbVie CRA after drug accountability has been completed at the study site.

In addition to overall drug accountability, the subject and study site will maintain subject dosing and subject drug accountability logs, [Appendix Q](#) and [Appendix R](#), respectively.

Non-investigational medicinal and other treatment products (standard of care) (e.g., wound care supplies) must be obtained commercially.

5.6 Discussion and Justification of Study Design

5.6.1 Discussion of Study Design and Choice of Control Groups

The design of this clinical trial is chosen to evaluate adalimumab in HS subjects with active HS lesions who require surgery as part of their standard care. Adalimumab will be compared to placebo during a 12-week period (Period A) prior to surgery, to assess the impact on all anatomic regions with active HS lesions including the HS surgical site and at least two other anatomical regions, one of which is Hurley Stage II or III. The impact on the HS surgical site will be also evaluated. Period B is a 2-week period during which the subject undergoes surgery and immediate post-operative routine care and monitoring. The utility of Period C, a 10-week period, is to assess the impact the adalimumab as compared to placebo in HS subjects who have undergone surgery, including the continued

impact on active HS lesions not within the surgical site (i.e., HS non-surgical sites) and the impact on the surgical wound. Previous clinical trials have not evaluated the use of adalimumab in concert with surgery. This study design will allow direct evaluation of adalimumab in a HS population that requires excisional surgery as part of their routine disease management. The placebo-controlled trial will allow a comparison of safety of adalimumab over a 24-week period including comparisons both before and after excisional surgery.

5.6.2 Appropriateness of Measurements

Standard statistical, clinical, and laboratory procedures will be used in this study. Efficacy measurements have been selected to assess disease activity in subjects with chronic HS. The primary efficacy endpoint (HiSCR, at least a 50% reduction in the AN count plus no increase in abscess count and no increase in draining fistulas) was designed and validated in the Adalimumab Clinical Development Program. The HiSCR has been accepted as a useful score to measure the impact of therapeutic agents in clinical trials as evidenced by the use of this measure in other clinical studies sponsored by entities other than AbbVie. All clinical and laboratory procedures in this study are standard and generally accepted.

5.6.3 Suitability of Subject Population

Males and females 18 years or older with moderate to severe HS requiring excisional surgery as part of routine disease management who meet all inclusion criteria but none of the exclusion criteria are eligible for this study. Adalimumab is approved for the treatment of active moderate to severe HS in adult patients who have not responded to conventional systemic HS therapy. This population in this study is similar to the moderate to severe HS population that was included in the Adalimumab Clinical Development Program, however this population will also have advanced HS lesions such that excisional surgery is required as part of their routine disease management. The population being studied represents normal clinical practice with a spectrum of subjects with high medical need due to great disability and discomfort. This ensures the activity of

adalimumab can be evaluated as part of the integrated medical-surgical management across a distribution of HS severity that has not been previously studied in a placebo-controlled clinical trial.

5.6.4 Selection of Doses in the Study

Adalimumab has been approved for the treatment of adult HS patients and the dose regimen used in this study will be the approved recommended dosing: 160 mg initially at Day 1, followed by 80 mg two weeks later at Day 15. Two weeks later (Day 29) continue with a dose of 40 mg every week as documented in the current SmPC.

6.0 Complaints

A Complaint is any written, electronic, or oral communication that alleges deficiencies related to the physical characteristics, identity, quality, purity, potency, durability, reliability, safety, effectiveness, or performance of a product/device after it is released for distribution.

The active study drug in this trial contains both a:

- biologic compound and
- pre-filled syringe

Complaints associated with any component of this study drug must be reported to the Sponsor (Section 6.2.2). For adverse events, please refer to Section 6.1. For product complaints, please refer to Section 6.2.

6.1 Medical Complaints

The Study Investigator will monitor each subject for clinical and laboratory evidence of AEs on a routine basis throughout the study. The Study Investigator will assess and record any AE in detail including the date of onset, event diagnosis (if known) or sign/symptom, severity, time course (end date, ongoing, intermittent), relationship of the AE to study drug, and any action(s) taken. For an SAE considered as having "no

reasonable possibility" of being associated with study drug, the Study Investigator will provide another cause of the event. For an AEs to be considered intermittent, the repetitive occurrences of the events must be of similar nature and severity. An AE, whether in response to a query, observed by study site personnel, or reported spontaneously by the subject will be recorded.

All AEs will be followed to a satisfactory conclusion.

6.1.1 Definitions

6.1.1.1 Adverse Event

An adverse event (AE) is defined as any untoward medical occurrence in a patient or clinical investigation subject administered a pharmaceutical product and which does not necessarily have a causal relationship with this treatment. An AE can therefore be any unfavorable and unintended sign (including an abnormal laboratory finding), symptom, or disease temporally associated with the use of a medicinal product, whether or not the event is considered causally related to the use of the product.

Such an event can result from use of the drug as stipulated in the protocol or labeling, as well as from accidental or intentional overdose, drug abuse, or drug withdrawal. Any worsening of a pre-existing condition or illness is considered an AE. Worsening in severity of a reported adverse event should be reported as a new AE. Laboratory abnormalities and changes in vital signs are considered to be AEs only if the event results in discontinuation from the study, necessitates therapeutic medical intervention, meets protocol specific criteria (see Section 6.1.7 regarding toxicity management) and/or if the Study Investigator considers the event to be an AE.

An elective surgery or procedure scheduled to occur during a study will not be considered an AE if the surgery or procedure is being performed for a pre-existing condition and the surgery/ or procedure has been pre planned prior to study entry. However, if the pre-existing condition deteriorates unexpectedly during the study (e.g., surgery performed

earlier than planned), then the deterioration of the condition for which the elective surgery/procedure is being done will be considered an AE.

In order to be eligible for this study a subject must require surgery due to HS and the surgery date will be determined after enrollment. The need for rescue surgery of the designated HS surgical site (i.e., surgery prior to Week 13) will not be recorded as an AE; rather the reason for surgery will be recorded on the appropriate eCRF as described in Section 5.3.2.4 and the subject will be withdrawn from the study.

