A further study examined the impact of pre-operative anti-TNF- α agents on postoperative outcomes 30 and 60 days after Crohn's disease surgery in a nationwide Danish cohort. Outcomes were death, reoperation, anastomosis leakage, intra-abdominal abscess and bacteraemia.⁴⁹ Among surgical procedures for Crohn's disease, 214 were exposed to anti-TNFs and 2079 were not. During the study period, infliximab counted for most of the anti-TNF- α agents given before surgery with 57.0% (122/214), adalimumab with 27.1% (58/214) and other anti-TNF- α agents with 15.9% (34/214).

The authors found no increased relative risks of death or abscess drainage 30 or 60 days after follow-up. Among exposed, 7.5% had a reoperation within 30 days vs. 8.6% among unexposed, adjusted odds ratio (OR) = 0.92, 95% confidence interval (CI): 0.52 – 1.63. Among exposed, 3.8% had an anastomosis leakage within 30 days after surgery vs. 2.8% among unexposed, adjusted OR = 1.33, 95% CI: 0.59 – 3.02. No further cases of anastomosis leakages appeared within 60 days.

Sub-analyses indicated no increased risk of bacteraemia after 30 days and no increased risks when anti-TNF- α agents were given 14 days before surgery.

In conclusion the authors found no significantly increased relative risks of post-operative complications after use of anti-TNF- α agents either 12 weeks or 14 days before surgery for Crohn's disease.

The safety and efficacy of adalimumab in HS has been explored in the Phase 2 trial (Study M10-467) and in two Phase 3 trials (Studies M11-313 and M11-810, PIONEER I and II, respectively). To date, 733 subjects with HS have been studied in adalimumab clinical studies in the HS clinical program, for a total of 836.3 patient-years of adalimumab exposure. Treatment emergent adverse events (TEAEs) were reported in 595 subjects (81.2%) for a rate of 417.6 events/100 patient-years. Worsening hidradenitis, nasopharyngitis, headache, and upper respiratory tract infection were the most frequently reported TEAEs.⁵⁰

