5.2.3.4 Rescue Therapy

If the Study Investigator, with agreement of the designated surgeon, determines the subject must undergo excision of the HS surgical site prior to the Week 13 study visit window (i.e., more than 7 days prior to the scheduled Week 13 study visit) all study

procedures scheduled for Week 12 must be performed and recorded, and the subject must be discontinued from the study.

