5.3.2.4 Measurement Methods

Serum concentrations of adalimumab will be determined using a validated assay methodology under the supervision of the AbbVie Drug Analysis Department.

Serum concentration of AAA will be determined using a validated assay methodology under the supervision of the AbbVie Drug Analysis Department.

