### 5.0 Analysis Populations and Important Subgroups

### 5.1 Analysis Population

The Intent-to-Treat (ITT) Population is defined as all subjects who randomised at the Baseline visit. The ITT Population will be used for the efficacy analysis. Of note, the surgery-related endpoints during Periods B and C will be analysed among the subjects who undergo surgery. Subjects in the ITT population will be analysed by treatment group as randomised.

In order to evaluate the impact of major protocol deviations on the primary efficacy endpoints, additional sensitivity analyses may be performed on a Per-protocol Population, which excludes subjects with major protocol deviations that potentially affect the primary efficacy endpoints. If it is decided that this analysis should be performed, the criteria for exclusion of subjects from the Per-protocol Population will be fully defined in the classification plan and the exclusion of subjects from the Per-protocol Population will be finalized before blind break and before the database lock.

The Safety Population is defined as all subjects who are in the ITT Population and receive at least one dose of study drug. The Safety Population in each period will be used for safety analysis. Of note, the surgery-related safety endpoints during Periods B and C will be analysed among the subjects who undergo surgery. Subjects in the Safety Population will be analysed by treatment group as treated.

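### Protocol 6.1.1.1 gives conflicting instructions on whether the HS deterioration behind a rescue excision is recorded as an AE, and such excisions fall outside the Period B/C surgery-related safety endpoints

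*Protocol*

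**What the plan says.** Protocol Section 6.1.1.1 contains three statements that bear on this.

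- General rule: "Any worsening of a pre-existing condition or illness is considered an AE".
- Pre-planned surgery is not itself an AE. If the underlying condition worsens unexpectedly, with earlier surgery given as the example, "then the deterioration of the condition for which the elective surgery/procedure is being done will be considered an AE".
- Trial-specific rule: "The need for rescue surgery of the designated HS surgical site (i.e., surgery prior to Week 13) will not be recorded as an AE". The same sentence goes on to name another place for the cause of the operation: "rather the reason for surgery will be recorded on the appropriate eCRF as described in Section 5.3.2.4". Such a subject also leaves the study.

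Protocol Section 5.2.3.4 (Rescue Therapy) covers the case where the investigator, with the surgeon's agreement, "determines the subject must undergo excision of the HS surgical site prior to the Week 13 study visit window". It requires the Week 12 procedures and discontinuation from the study.

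SAP Section 5.1, like Protocol Section 8.1.1, says that "the surgery-related safety endpoints during Periods B and C will be analysed among the subjects who undergo surgery".

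**The concern.** An excision brought forward because HS has worsened is the very example that the second statement uses to make the deterioration an AE. The third statement addresses the same event and moves its reason to another form. In many rescue cases the reason will be the deterioration itself, so the two paragraphs point a site in different directions.

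The event is not marginal. Protocol Section 3.6 reports from the earlier HS programme that "Worsening hidradenitis, nasopharyngitis, headache, and upper respiratory tract infection were the most frequently reported TEAEs". If sites apply the last paragraph literally, milder HS worsening is tabulated while worsening bad enough to force excision and withdrawal may not be. Rescue depends on outcome, so any loss could differ between arms, and sites could differ from one another. Separately, the surgery-related safety endpoints are tied to periods that a subject rescued in Period A never enters.

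**Working it through.** The plan gives no figure to reproduce. The check is a comparison of passages.

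1. **Can the two paragraphs of Protocol 6.1.1.1 be reconciled?** Yes, by separating the operation (not an AE) from the deterioration (an AE). The text does not say this. It exempts the need for surgery, and its contrast between the AE record and the other eCRF page reads as a replacement rather than an addition.

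2. **Does the cross-reference settle it?** No. Section 5.3.2.4 is headed Measurement Methods and begins "Serum concentrations of adalimumab will be determined using a validated assay methodology". It says nothing about rescue surgery.

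3. **Does the rescue section settle it?** No. Section 5.2.3.4 names no eCRF page for the reason and gives no AE rule. It also draws a different line: more than 7 days before the scheduled Week 13 visit, against any time before Week 13 in 6.1.1.1. An excision in the last 7 days before that visit is rescue under one section and not under the other.

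4. **Does the SAP settle it?** No. Section 4.7 lists discontinuation for an AE of worsening HS and planned surgery done before Week 13 as alternatives. That shows some HS worsening is expected on AE forms and that early surgery can be identified. It does not show that a rescued subject also has an AE entered.

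5. **What follows if the deterioration is not entered?** Section 6.1.1.2 defines an SAE as an AE that meets a seriousness criterion. Without the AE there can be no SAE and no AE leading to discontinuation, so the event is absent from the summaries in Protocol 8.1.5 and SAP 7.2.

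6. **What happens to complications of the rescue excision?** Section 6.1.1.1 does not exempt them. Section 6.1.4 collects all AEs until the call about 70 days after study drug stops, or until commercial adalimumab starts. Section 6.1.1.3 has surgical-site AEs collected and analysed, with no tie to Week 13. SAP 7.2 counts onset within 70 days of the last dose as treatment-emergent. They stay in the AE and SAE data.

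7. **Are they in the surgery-related safety endpoints?** No. Those are defined for Periods B and C, and a subject rescued in Period A has been withdrawn. Protocol 8.1.5 promises a summary of surgical-site AEs, but SAP 7.2 does not list one.

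8. **Size.** Events lost per arm = subjects per arm × rescue rate × share of deteriorations not recorded. Only the first is given (about 100). One lost event is 1/100 = 1 percentage point. If rescue is assumed at 2% to 10%, the ceiling is 100 × 0.02 × 1 = 2 to 100 × 0.10 × 1 = 10 per arm, reached only if no site records the deterioration. The floor is 0, if every site does.

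**The case against.** The strongest reply is that only the procedure is exempt. The general rule on worsening is never withdrawn, and SAP 4.7 expects AEs of worsening HS, so a careful site would record both the AE and the reason for surgery. Early surgery is not hidden either: its reason is captured, the subject is withdrawn, and SAP 4.7 assigns an unfavourable value for ranked secondary endpoints 3 and 4. Exclusion criterion 3 removes subjects judged at entry to need surgery before Week 13, which should keep rescue uncommon. SAP 7.2 plans no tests on AEs, so no p-value planned there is affected.

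Most of this stands, and it limits the point to a possible loss of unknown size. It does not remove the ambiguity, because the reading it relies on has to be supplied by the site.

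A reader might go further and infer that complications of rescue surgery also disappear from the AE and SAE data. The documents do not support that: the 70-day collection and treatment-emergent windows keep them in.

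A reader might also infer that the Period B/C comparison is biased because rescued subjects are left out. That does not follow. The secondary objective concerns adalimumab continued through and after surgery, and rescued subjects are discontinued. Pooling their excisions with planned ones would answer a different question.

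**Conclusion.** The point holds as an unresolved conflict in a recording rule, with a gap in the surgical-safety display. A site that follows the last paragraph of Protocol 6.1.1.1 may leave the HS deterioration off the AE page, which would remove it from the treatment-emergent AE, SAE and AE-discontinuation summaries. The documents do not say that it must be left off, so the loss is possible rather than certain. Its size cannot be stated: there is no rescue rate in the documents, and the 2 to 10 events per arm above is a ceiling under assumed rates with no site recording the event.

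Every rescue excision in Period A is outside the Period B/C surgery-related endpoints, but its complications remain in the general AE data until about 70 days after the last dose or the start of commercial adalimumab.

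The correction should be made because it is cheap and the data at risk are severe, outcome-dependent events.

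**What to change.** 1. In the last paragraph of Protocol 6.1.1.1, state that the rescue operation itself is not an AE, but the deterioration that prompted it is recorded as an AE, and as an SAE if it meets Section 6.1.1.2. This brings it into line with the paragraph above it.
2. Replace the pointer to Section 5.3.2.4 with the place where the reason for rescue surgery is actually recorded.
3. Reconcile the rescue boundary in 6.1.1.1 with that in 5.2.3.4. No view is offered here on which is right.
4. In SAP 5.1 and 7.2, add a separate summary of surgical-site AEs after any post-dose excision of the HS surgical site done before Period B. Leave the planned-surgery analysis for Periods B and C as it is.

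The cost is a few sentences in the protocol and SAP, one extra summary, and a few more AE forms. Reported counts of HS-worsening AEs may rise slightly.
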